5.2.2 Specify inclusion/exclusion criteria for cohort entry and define the index date

Inclusion and exclusion criteria were adapted from the trial as closely as possible. Definitions for all inclusion/exclusion are provided in **Appendix A** and are summarized in the flowcharts below.

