5.3 Flowchart of the study cohort assembly

	OPTUM		MARKETSCAN	
	Less Excluded	Remaining	Less Excluded	Remaining
	Patients	Patients	Patients	Patients
All patients		79,335,559		200,203,908
Did not meet cohort entry criteria	-77,381,938	1,953,621	-196,683,354	3,520,554
Excluded due to insufficient enrollment	-308,951	1,644,670	-522,438	2,998,116
Excluded due to prior use of referent	-274,142	1,370,528	-362,567	2,635,549
Excluded due to prior use of exposure	-641,980	728,548	-1,225,388	1,410,161
Excluded because patient qualified in >1 exposure category	-10,386	718,162	-17,868	1,392,293

Excluded based on Missing/Unknown Age	-6	718,156	-1	1,392,292
Excluded based on Missing/Unknown Gender	-125	718,031	0	1,392,292
Excluded based on Inclusion #1 - Age 40 to 80 years old	-5	718,026	0	1,392,292
Excluded based on Inclusion #3a - Diagnosis of COPD	-471,394	246,632	-1,038,792	353,500
Excluded based on Inclusion #3b - Clinical history of at least 1 COPD Exacerbation	-110,352	136,280	-153,003	200,497
Excluded based on Exclusion #1 - COPD exacerbation in the 6 weeks prior	-33,666	102,614	-34,019	166,478
Excluded based on Exclusion #2a - Current asthma	-13,344	89,270	-13,539	152,939
Excluded based on Exclusion #2b - Current eczema, atopic dermatitis and/or allergic rhinitis	-5,978	83,292	-7,929	145,010
Excluded based on Exclusion #3 - Has a known respiratory disorder other than COPD	-15,367	67,925	-20,732	124,278
Excluded based on Exclusion #4 - Has narrow-angle glaucoma, prostatic hyperplasia or				
obstruction of the neck of the bladder	-3,927	63,998	-5,648	118,630
Excluded based on Exclusion #5 - Has undergone lung transplantation and/or lung volume				
reduction	-11	63,987	-41	118,589
Excluded based on Exclusion #7 - Requires regular (daily) long-term oxygen therapy (LTOT)	-2,422	61,565	-1,401	117,188
Excluded based on Exclusion #8 - Is receiving beta-blockers (except eye drops)	-7,770	53,795	-14,196	102,992
Excluded based on Exclusion #11 - Has evidence of alcohol, drug or solvent abuse	-945	52,850	-793	102,199
Excluded based on Exclusion #14 - Exclude use of Salmeterol, tiotropium, and fluticasone				
containing inhaler use	-591	52,259	-819	101,380
Final cohort		52,259		101,380

6 Variables

6.1 Exposure-related variables:

Study drug:

The study exposure of interest is initiation of SFC (LABA/ICS combination). Initiation will be defined by no use of inhaled SFC during the prior 180 days before treatment initiation (washout period).

Comparator agents:

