	Aim: To evaluate the effect of tiotropium compared to SFC on healthcare utilization of COPD exacerbations	Exposure: SFC Reference: Tiotropium		claims
	PRIMARY OUTCOME			Poor mapping or cannot be measured in claims
		Measured 1 day after drug initiation in primary diagnosis position and inpatient care setting		
	Primary endpoint: Healthcare utilization COPD exacerbation rate	COPD (Inpatient, Primary) ICD-9 Diagnosis: 491.x, 492.x, 496 ICD-10 Diagnosis: J41.x, J42, J43.x, J44.x OR Measured 1 day after drug initiation in any diagnosis position any care setting AND steriod use within 14 days COPD (Any care setting, Any position) ICD-9 Diagnosis: 491.x, 492.x, 496 ICD-10 Diagnosis: J41.x, J42, J43.x, J44.x AND Corticosteriod systemic administration and/or oral prescription of: - Prednisone - Prednisolone - Methylprednisolone - Dexamethasone - Hydrocortisone		Can't be measured in claims but not important for the analysis
	Tiotropium 18 mcg once daily vs. SFC 50/500 r			
	· · · · · · · · · · · · · · · · · · ·	Age 40 to 80 years old at the time of drug initiation		
2	Smoking history of ≥ 10 pack years			
3a	Diagnosis of COPD	Measured from the start of all available data to and including the day of drug initiation in any diagnosis position and in the inpatient and outpatient care setting COPD ICD-9 Diagnosis: 491.x, 492.x, 496 ICD-10 Diagnosis: J41.x, J42, J43.x, J44.x		

3b	Clinical history of at least 1 COPD exacerbation	Measured since all available data to 43 days prior to drug initiation in primary diagnosis position and inpatient care setting COPD (Inpatient, Primary) ICD-9 Diagnosis: 491x, 492.x, 496.0 ICD-10 Diagnosis: J41, J42.x, J43.x, J44.x OR Measured since all available data to 43 days prior to drug initiation in any diagnosis position, inpatient and outpatient care setting AND steriod use within 30 days COPD ICD-9 Diagnosis: 491.x, 492.x, 496.0 ICD-10 Diagnosis: J41.x, J42, J43.x, J44.x AND Corticosteriod systemic administration and/or prescription - Prednisone - Prednisolone - Methylprednisolone - Methylprednisolone - Dexamethasone
4	Post bronchodilator FEV1 of < 50% of predicted normal	- Hydrocortisone
5	FEV1 / FVC ratio <70%	
6	Reversibility to 400 mcg albuterol of less or equal to 10% of predicted FEV1 at Visit 1	
7	A score of 2 or more on the Modified Medical Research Council dyspnea scale	
8	Free from exacerbation in the 6 weeks prior to screening	Included in the exclusion criteria
	EXCLUSION CRITERIA	

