		ICD-9 Diagnosis: 365.02, 36s.06, 365.2x
		ICD-10 Diagnosis: H40.03x, H40.2xx,
		Prostatic hyperplasia or obstruction of the neck of the bladder
I	Ulas paranu anala glaupama mastatia humanalasia ar abstruction of the mak of the hadder that in the continue of the	
4	Has narrow-angle glaucoma, prostatic hyperplasia or obstruction of the neck of the bladder that in the opinion of the	ICD-9 Diagnosis: 600.x
	investigator should prevent the subject from entering the study	ICD-10 Diagnosis: N40.x
		OR
		[
		At least one 30-day supply presciption claims for oral:
		Alfuzosin, doxazosin, tamsulosin, silodosin, finasteride 5 mg, dutasteride
ь		

[figure not shown]
_		Measured since all available data to and including the day of drug initiation in any diagnosis
		position in the inpatient and outpatient care setting
		Lung transplant
		ICD-9 Diagnosis: V42.6, 996.84
		ICD-10 Diagnosis: Z94.2, T86.810, T86.811, T86.819
		ICD-9 Procedure: 33.5x ICD-10 Procedure: OBYMOZO, OBYMOZ1, OBYMOZ2, OBYKOZO, OBYKOZ1, OBYKOZ2, OBYLOZO,
		OBYLOZ1, OBYLOZ2
5	Has undergone lung transplantation and/or lung volume reduction	CPT-4 Code: 32850 - 32856
		Lung volume reduction surgery (LVRS) ICD-9 Procedure: 32.22, 32.3x
		ICD-10 Procedure: 0BBC0ZZ, 0BBC4ZZ, 0BBD0ZZ, 0BBD4ZZ, 0BBF0ZZ, 0BBF4ZZ, 0BBG0ZZ,
		OBBG4ZZ, OBBH0ZZ, OBBH4ZZ, OBBJ0ZZ, OBBJ4ZZ, OBBK0ZZ, OBBK4ZZ, OBBL0ZZ, OBBL4ZZ,
		OBBMOZZ, OBBM4ZZ
		CPT/HCPCS codes: 32491, 32672, G0302, G0303, G0304, G0305
6	Female who is a nursing mother	
		Measured since all available data to and including the day of drug initiation in any diagnosis
		position in the inpatient and outpatient care setting
		LTOT
7	Requires regular (daily) long-term oxygen therapy (LTOT)	ICD-9 Diagnosis: V46.2
		ICD-10 Diagnosis: Z99.81
		CPT/HCPCS code: E0424, E0441, E0443
		Measured 180 days prior to and including the day of drug initiation with prescription for oral:
		Acebutolol, Atenolol, Betaxolol, Bisoprolol, Carteolol, Carvedilol, Labetalol, Metoprolol,
8	Is receiving beta-blockers (except eye drops)	Metiranolol, Nebivolol, Nadolol, Propranolol, Pindolol, Sotalol, Penbutolol, Oxprenolol
9	Has a serious, uncontrolled disease likely to interfere with the study	
10	Has received any other investigational drugs within the 4 weeks prior to Visit 1	
		Measured 180 days prior to and including the day of drug initiation in any diagnosis position in
		the inpatient and outpatient care setting
		Alcohol Abuse or Dependence

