		ICD-9 diagnosis: 291.xx, 303.xx, 305.0x, 571.0x, 571.1x, 571.2x, 571.3x, 357.5x, 425.5x, E860.0x,
		V11.3x
11	Has, in the opinion of the investigator, evidence of alcohol, drug or solvent abuse	ICD-10 diagnosis: F10.x, K70.x, G62.1, I42.6, 099.31x
		Drug Abuse or Dependence
		ICD-9 diagnosis: 292.xx, 304.xx, 305.2x-305.9x, 648.3x ICD-10 diagnosis: F11.x, F12.x, F13.x, F14.x, F15.x, F16.x, F17.2x, F18.x, F19.x, F55.2, G62.0,
		099.32x
		U99.32X
		099.52X
12	Has a known or suspected hypersensitivity to beta2-agonists, inhaled corticosteroids, anticholinergic agents or any components of the formulations (e.g. lactose or milk protein)	U99.32X

		Measured 180 days prior to and including the day of drug initiation in prescription claims
13	Exclude use of Salmeterol, tiotropium, and fluticasone containing inhaler use within 180 days prior to CED	Brand names - STIOLTO RESPIMAT SEREVENT SEREVENT DISKUS ARNUITY ELLIPTA BREO ELLIPTA TRELEGY ELLIPTA FLOVENT HFA FLOVENT DISKUS ARMONAIR RESPICLICK ARMONAIR
		OR Generic name -
		TIOTROPIUM BROMIDE/OLODATEROL HCL SALMETEROL XINAFOATE

Optum MarketScan

[figure not shown]
BEFORE PS MATCHING

[figure not shown]

The c-statistics for the propensity score model, pre-matching was 0.689. The post-matching c-statistic was 0.523.

The c-statistics for the propensity score model, pre-matching was 0.7. The post-matching c-statistic was 0.516.

UNMATCHED

UNIVIATCHED		ODTUM			MADVETCCAN			POOLED			
		OPTUM			MARKETSCAN			POOLED			
	Referent - Tiotropium	Exposure - Salmeterol/Fluticasone	St. Diff	Referent - Tiotropium	Exposure - Salmeterol/Fluticasone	St. Diff	Referent - Tiotropium	Exposure - Salmeterol/Fluticasone	St. Diff		
Number of patients	21,689	30,570	St. DITT	36,727	64,653	St. DITT	58,416	95,223	St. DITT		
Calendar Time - Year of Initiation (2004 - 2020)	21,089	30,370		30,727	64,633		38,416	95,225			
2004-2006; n (%)	1,330 (6.1%)	3,505 (11.5%)	-0.1915	5,640 (15.4%)	15,357 (23.8%)	-0.2128	6,970 (11.9%)	18,862 (19.8%)	-0.218		
2007-2008; n (%)	2,190 (10.1%)	3,669 (12.0%)	-0.0606	5,594 (15.2%)	11,223 (17.4%)	-0.0596	7,784 (13.3%)	14,892 (15.6%)	-0.065		
2009-2011; n (%)	4,060 (18.7%)	6,299 (20.6%)	-0.0478	9,988 (27.2%)	17,461 (27.0%)	0.0045	14,048 (24.0%)	23,760 (25.0%)	-0.023		
2012-2015; n (%)	6,704 (30.9%)	8,124 (26.6%)	0.0951	11,489 (31.3%)	15,233 (23.6%)	0.1732	18,193 (31.1%)	23,357 (24.5%)	0.148		
2016-2018; n (%)	5,091 (23.5%)	6,116 (20.0%)	0.0849	4,016 (10.9%)	5,379 (8.3%)	0.0883	9,107 (15.6%)	11,495 (12.1%)	0.101		

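### Exclusion 11 lists F17.2x among its ICD-10 codes but skips 305.1 in the ICD-9 305 block, so as written the rule changes with the coding era and departs from the trial criterion

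*Combined protocol and SAP*

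**What the plan says.** Section 5.2.2 states the aim for eligibility: "Inclusion and exclusion criteria were adapted from the trial as closely as possible". It refers the reader to Appendix A for all definitions.

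In the Appendix A table, the trial criterion emulated by Exclusion 11 is "Has, in the opinion of the investigator, evidence of alcohol, drug or solvent abuse". The look-back is "Measured 180 days prior to and including the day of drug initiation in any diagnosis position in" inpatient or outpatient care. Two code groups implement it:

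- Alcohol, ICD-9: "ICD-9 diagnosis: 291.xx, 303.xx, 305.0x, 571.0x, 571.1x, 571.2x, 571.3x, 357.5x, 425.5x, E860.0x" and V11.3x. The ICD-10 counterpart begins with F10.x.
- Drugs, ICD-9: "ICD-9 diagnosis: 292.xx, 304.xx, 305.2x-305.9x, 648.3x". The ICD-10 counterpart includes "F11.x, F12.x, F13.x, F14.x, F15.x, F16.x, F17.2x, F18.x, F19.x, F55.2, G62.0".

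Inclusion 2 of the trial, in the same table, is "Smoking history of ≥ 10 pack years"; its implementation cell is empty. Smoking does appear as a baseline covariate in Appendix B, without the asterisk that marks variables left out of the propensity score model.

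The section 5.3 flowchart has one row for this step, "Excluded based on Exclusion #11 - Has evidence of alcohol, drug or solvent abuse", with 945 removals in Optum and 793 in MarketScan.

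**The concern.** The criterion covers alcohol, drugs and solvents, and says nothing of tobacco. The ICD-9 lists agree with that: they take in the whole 305 block except 305.1. The ICD-10 lists run from F10 to F19 and do not step over F17. One criterion therefore has two meanings depending on when a patient entered. Cohort entry runs from January 2004 to December 2018 in MarketScan and to March 2020 in Optum, so both code systems are in use.

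Fidelity to the target population and consistency across calendar time are at stake. The emulated trial required a substantial smoking history, so removing patients because nicotine dependence was recorded runs against the population it enrolled. Only patients with an F17.2x record in the 180-day window are affected; smokers without that record stay eligible.

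**Working it through.** **1. Code lists side by side (Appendix A, Exclusion 11).**

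| Block | Covered | Not covered |
|---|---|---|
| ICD-9 305 | 305.0x (alcohol list), 305.2x to 305.9x (drug list) | 305.1 |
| ICD-10 F10 to F19 | F10.x (alcohol list); F11.x to F16.x, F17.2x, F18.x, F19.x (drug list) | F17 codes outside F17.2x |

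The statement that only 305.1 is missing applies to the 305 block. It does not mean the lists match elsewhere; for example, G62.0 has no evident partner in the ICD-9 drug list.

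**2. Flowchart (section 5.3).** The plan's figures reproduce:

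- Optum: 53,795 − 945 = 52,850
- MarketScan: 102,992 − 793 = 102,199

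**3. Ceiling on the effect as executed.** The flowchart does not split Exclusion 11 by code or year, so the ceiling is every removal at that step:

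- 945 + 793 = 1,738
- 53,795 + 102,992 = 156,787
- 1,738 / 156,787 = 1.1%

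By database this is 945 / 53,795 = 1.8% and 793 / 102,992 = 0.8%.

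**4. Could the code have been run?** Take entry from 2016 onward as the ICD-10 period (an assumption; the document gives no switch date). From the unmatched table in Appendix B, the retained entrants in that period are:

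- Optum: 5,091 + 6,116 + 2,314 + 2,857 = 16,378, or 31.3% of 52,259
- MarketScan: 4,016 + 5,379 = 9,395, or 9.3% of 101,380

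If every Exclusion 11 removal were due to F17.2x, its prevalence among entrants reaching this step in those years would be at most removals / (removals + retained):

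| Scenario | Optum | MarketScan |
|---|---|---|
| All removals due to F17.2x | 945 / 17,323 = 5.5% | 793 / 10,188 = 7.8% |
| Same, with all Exclusion 14 removals (591; 819) placed in the period | 945 / 17,914 = 5.3% | 793 / 11,007 = 7.2% |
| Half the removals due to alcohol or other drugs (assumption) | 472.5 / 16,850.5 = 2.8% | 396.5 / 9,791.5 = 4.0% |

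In the other direction, a prevalence p removes retained × p / (1 − p). At p = 5% this gives 862 (Optum) and 494 (MarketScan), which fits within the reported 945 and 793. At p = 10% it gives 1,820 and 1,044, which does not. The actual F17.2x prevalence is not reported.

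**5. Balance after matching (Appendix B, pooled).** Smoking is 20.2% on tiotropium and 19.6% on SFC (standardised difference 0.015). Standardised differences for calendar period are at most 0.016 in either database or pooled.

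**The case against.** The strongest objection is that the code may never have been run. After Exclusion 11, the unmatched cohort still contains 6,731 + 5,954 = 12,685 of 52,259 Optum patients (24.3%) and 6,588 + 6,674 = 13,262 of 101,380 MarketScan patients (13.1%) with a smoking flag, while all Exclusion 11 codes over all years removed only 945 and 793. A slip confined to the published list is a serious possibility, and the cohort would then have no defect. The codes behind the smoking flag are not given, and a 5% prevalence fits the counts, so the question stays open.

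Two further points carry weight. The meanings of F17.2x and 305.1 come from the code sets, not from the document; what can be seen on the page is the asymmetry. Also, the Appendix A table points to an external folder for further detail and grades each mapping by colour. Neither can be seen in the text available here, so the absence of a rationale is established only for that text.

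It is also fair that the consequence is small. The ceiling is 1.1%, the stated power is essentially 1 in section 10, and nothing shows bias between arms. These points limit the size of the finding. They do not reconcile the two lists with each other or with the criterion.

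**Conclusion.** The concern holds and is minor. Followed exactly, Appendix A excludes patients for a tobacco code in the ICD-10 years but not in the ICD-9 years, under a criterion that does not name tobacco and in an emulation of a trial that required a smoking history.

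The effect on the cohort as built lies between none, if F17.2x was not executed, and at most 1,738 patients (1.1% of those reaching the step). The true figure must fall below that ceiling by the number removed for alcohol or other drugs alone.

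The conclusion rests on the standard meanings of the two codes. The prevalence limits rest also on treating 2016 onward as the ICD-10 period. If ICD-10 coding reached into the 2012–2015 stratum, those limits would fall.

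Something needs correcting in either case. If the code was run, the later part of the cohort departs from the stated criterion. If it was not, the published list misdescribes what was done, and anyone repeating the study from it would build a different cohort.

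**What to change.** Check the executed query; section 2 says the implementation history is archived in the platform. Delete F17.2x from Exclusion 11 so that both coding eras exclude alcohol and non-tobacco drugs only, and keep tobacco codes for the smoking covariate.

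- If the executed query contained F17.2x, re-run the cohort and the matching, and report the Exclusion 11 row with and without the code, preferably by coding era.
- If it did not, correct the published list and state that the cohort is unchanged.

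The certain cost is one deleted code and one look at the archive. A re-run, if needed, would return at most 1,738 patients before Exclusion 14 and matching.

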PRX - Antibiotics treatment (30 days to CED); n (%)	3,096 (14.3%) 6.911 (31.9%)	5,872 (19.2%)	-0.1315 -0.0107	6,246 (17.0%)	14,851 (23.0%) 20.935 (32.4%)	-0.1504	9,342 (16.0%) 18,504 (31.7%)	20,723 (21.8%) 30,848 (32.4%)	-0.149 -0.015
PRX - Systemic Corticosteroids (with CPT) (180 days to 31 days before CED); n (%) PRX - Systemic Corticosteroids (with CPT) (30 days to CED); n (%)	1,106 (5.1%)	9,913 (32.4%) 3,126 (10.2%)	-0.0107	11,593 (31.6%) 2,576 (7.0%)	8,168 (12.6%)	-0.0172	3,682 (6.3%)	11,294 (11.9%)	-0.015
PRX - Roflumilast; n (%)	67 (0.3%)	42 (0.1%)	0.0448	162 (0.4%)	76 (0.1%)	0.0601	229 (0.4%)	118 (0.1%)	0.060
PRX - ROHUHHIIdSC, II (%)	67 (0.3%)	42 (0.1%)	0.0448	182 (0.4%)	76 (0.1%)	0.0001	223 (0.470)	110 (0.170)	0.000
CVD - Unstable angina/MI; n (%)	593 (2.7%)	643 (2.1%)	0.0392	701 (1.9%)	1,029 (1.6%)	0.0229	1,294 (2.2%)	1,672 (1.8%)	0.029
CVD - Stable Angina ; n (%)	403 (1.9%)	486 (1.6%)	0.0229	573 (1.6%)	834 (1.3%)	0.0251	976 (1.7%)	1,320 (1.4%)	0.024
CVD - Any Heart failure (HF) ; n (%)	1,334 (6.2%)	1,649 (5.4%)	0.0342	2,076 (5.7%)	3,132 (4.8%)	0.0404	3,410 (5.8%)	4,781 (5.0%)	0.035
CVD - Atrial fibrillation; n (%)	1,091 (5.0%)	1,261 (4.1%)	0.0432	1,764 (4.8%)	2,458 (3.8%)	0.0493	2,855 (4.9%)	3,719 (3.9%)	0.049
CVD - Other dysrythmias ; n (%)*	1,576 (7.3%)	1,894 (6.2%)	0.0439	2,195 (6.0%)	3,210 (5.0%)	0.0439	3,771 (6.5%)	5,104 (5.4%)	0.047
CVD - Valve disorder ; n (%)	277 (1.3%)	332 (1.1%)	0.0184	336 (0.9%)	612 (0.9%)	0.0000	613 (1.0%)	944 (1.0%)	0.000
CVD - Implantable cardioverter defibrillator ; n (%)*	69 (0.3%)	82 (0.3%)	0.0000	111 (0.3%)	109 (0.2%)	0.0200	180 (0.3%)	191 (0.2%)	0.020
CVD - CABG/PCI; n (%)	521 (2.4%)	534 (1.7%)	0.0494	464 (1.3%)	595 (0.9%)	0.0384	985 (1.7%)	1,129 (1.2%)	0.042
CVD - Coronary atherosclerosis and other forms of chronic ischemic heart disease; n (%)	2,581 (11.9%)	2,968 (9.7%)	0.0709	4,121 (11.2%)	5,577 (8.6%)	0.0871	6,702 (11.5%)	8,545 (9.0%)	0.082
CVD - Stroke/TIA ; n (%)	641 (3.0%)	713 (2.3%)	0.0436	943 (2.6%)	1,546 (2.4%)	0.0128	1,584 (2.7%)	2,259 (2.4%)	0.019
CVD - Peripheral Vascular Disease (PVD) or PVD Surgery; n (%)	1,693 (7.8%)	1,661 (5.4%)	0.0968	1,776 (4.8%)	2,384 (3.7%)	0.0545	3,469 (5.9%)	4,045 (4.2%)	0.078
CVD - Hyperlipidemia ; n (%)	9,573 (44.1%)	12,176 (39.8%)	0.0872	10,218 (27.8%)	15,419 (23.8%)	0.0915	19,791 (33.9%)	27,595 (29.0%)	0.106
CVD - Hypertension; n (%)	11,323 (52.2%)	14,593 (47.7%)	0.0901	13,871 (37.8%)	21,783 (33.7%)	0.0856	25,194 (43.1%)	36,376 (38.2%)	0.100
CRX - ACEi or ARB; n (%)	8,168 (37.7%)	11,243 (36.8%)	0.0186	13,292 (36.2%)	22,744 (35.2%)	0.0209	21,460 (36.7%)	33,987 (35.7%)	0.021
CRX - Mineralocorticoid receptor antagonist ; n (%)	325 (1.5%)	516 (1.7%)	-0.0159	778 (2.1%)	1,227 (1.9%)	0.0143	1,103 (1.9%)	1,743 (1.8%)	0.007
CRX - Loop or Thiazide diuretics; n (%)	4,670 (21.5%)	6,398 (20.9%)	0.0147	8,382 (22.8%)	14,759 (22.8%)	0.0000	13,052 (22.3%)	21,157 (22.2%)	0.002
CRX - Statins and other lipid lowering agents; n (%)	8,977 (41.4%)	11,512 (37.7%)	0.0757	14,474 (39.4%)	23,089 (35.7%)	0.0765	23,451 (40.1%)	34,601 (36.3%)	0.078
CRX - CCB and other antihypertensives; n (%)	4,813 (22.2%)	6,332 (20.7%)	0.0365	8,069 (22.0%)	13,275 (20.5%)	0.0367	12,882 (22.1%)	19,607 (20.6%)	0.037
CRX - Digoxin ; n (%)*	314 (1.4%)	440 (1.4%)	0.0000	923 (2.5%)	1,584 (2.5%)	0.0000	1,237 (2.1%)	2,024 (2.1%)	0.000
CRX - Nitrates; n (%)*	702 (3.2%)	908 (3.0%)	0.0115	1,615 (4.4%)	2,613 (4.0%)	0.0199	2,317 (4.0%)	3,521 (3.7%)	0.016
			0.0000			0.0000	40.640.440.20()	47.360 (40.40)	0.002
OCM-Type1 or 2 DM; n (%)	4,453 (20.5%)	6,394 (20.9%)	-0.0099 -0.0043	6,166 (16.8%)	10,874 (16.8%)	0.0000	10,619 (18.2%)	17,268 (18.1%)	0.003
OCM - Occurrence of Diabetic retinopathy/nephropathy/neuropathy; n (%)*	1,266 (5.8%)	1,801 (5.9%)		1,080 (2.9%)	1,727 (2.7%)	0.0121 0.0294	2,346 (4.0%)	3,528 (3.7%) 1,459 (1.5%)	0.016
OCM - Hypertensive nephropathy; n (%)*	689 (3.2%)	848 (2.8%)	0.0235	453 (1.2%)	611 (0.9%)		1,142 (2.0%)		
OCM - Hypotension ; n (%)* OCM - Hyperkalemia ; n (%)*	383 (1.8%) 210 (1.0%)	423 (1.4%) 269 (0.9%)	0.0319	466 (1.3%) 219 (0.6%)	621 (1.0%) 297 (0.5%)	0.0281	849 (1.5%) 429 (0.7%)	1,044 (1.1%) 566 (0.6%)	0.035 0.012
OCM - Hyperkalemia ; n (%)* OCM - CKD II, III, or IV; n (%)	1,196 (5.5%)	1,533 (5.0%)	0.0103	665 (1.8%)	968 (1.5%)	0.0135	1,861 (3.2%)	2,501 (2.6%)	0.012
OCM - HD/PD/ESRD; n (%)*	73 (0.3%)	96 (0.3%)	0.0000	155 (0.4%)	268 (0.4%)	0.0000	228 (0.4%)	364 (0.4%)	0.000
	2,569 (11.8%)		0.0000		· · ·	0.0000	6,212 (10.6%)	9,069 (9.5%)	0.000
OCM - Osteoporosis; n (%) OCM - Sleep apnea ; n (%)	2,011 (9.3%)	3,180 (10.4%) 2,533 (8.3%)	0.0353	3,643 (9.9%) 3,369 (9.2%)	5,889 (9.1%) 4,832 (7.5%)	0.0615	5,380 (9.2%)	7,365 (7.7%)	0.054
OCM - Fractures ; n (%)	939 (4.3%)	1,250 (4.1%)	0.0100	1,631 (4.4%)	2,887 (4.5%)	-0.0048	2,570 (4.4%)	4,137 (4.3%)	0.005
OCM - Other Arthritis, Arthropathies and Musculoskeletal Pain ; n (%)	7,847 (36.2%)	11,143 (36.5%)	-0.0062	11,173 (30.4%)	20,027 (31.0%)	-0.0130	19,020 (32.6%)	31,170 (32.7%)	-0.002
OCM - Dorsopathies; n (%)	6,114 (28.2%)	8,136 (26.6%)	0.0359	8,276 (22.5%)	13,884 (21.5%)	0.0241	14,390 (24.6%)	22,020 (23.1%)	0.035
OCM - Gout (acute/chronic); n (%)*	143 (0.7%)	251 (0.8%)	-0.0116	278 (0.8%)	437 (0.7%)	0.0116	421 (0.7%)	688 (0.7%)	0.000
OCM - Hyperthyroidism ; n (%)*	136 (0.6%)	171 (0.6%)	0.0000	179 (0.5%)	286 (0.4%)	0.0149	315 (0.5%)	457 (0.5%)	0.000
OCM - Hypothyroidism ; n (%)*	2,033 (9.4%)	2,899 (9.5%)	-0.0034	2,650 (7.2%)	4,532 (7.0%)	0.0078	4.683 (8.0%)	7,431 (7.8%)	0.007
OCM - VTE : n (%)*	400 (1.8%)	502 (1.6%)	0.0155	663 (1.8%)	1,090 (1.7%)	0.0076	1,063 (1.8%)	1,592 (1.7%)	0.008
OCM - GERD ; n (%)	3,134 (14.4%)	3,995 (13.1%)	0.0378	2,891 (7.9%)	4,522 (7.0%)	0.0343	6,025 (10.3%)	8,517 (8.9%)	0.048
OCM-Cancer :n (%)	2.248 (10.4%)	2,942 (9.6%)	0.0267	3.071 (8.4%)	4,758 (7.4%)	0.0371	5,319 (9.1%)	7,700 (8.1%)	0.036
OCM - Hypovolemia/volume depletion ; n (%)*	468 (2.2%)	601 (2.0%)	0.0139	622 (1.7%)	1,021 (1.6%)	0.0079	1,090 (1.9%)	1,622 (1.7%)	0.015
OCM-Anemia; n (%)	2,185 (10.1%)	3,009 (9.8%)	0.0100	2,840 (7.7%)	4,754 (7.4%)	0.0114	5,025 (8.6%)	7,763 (8.2%)	0.014
OCM - Dementia ; n (%)*	777 (3.6%)	968 (3.2%)	0.0221	887 (2.4%)	1,320 (2.0%)	0.0273	1,664 (2.8%)	2,288 (2.4%)	0.025
OCM - Depression ; n (%)	3,467 (16.0%)	4,284 (14.0%)	0.0560	3,580 (9.7%)	5,735 (8.9%)	0.0275	7,047 (12.1%)	10,019 (10.5%)	0.051
ORX - Metformin; n (%)*	2,200 (10.1%)	3,182 (10.4%)	-0.0099	3,134 (8.5%)	5,875 (9.1%)	-0.0212	5,334 (9.1%)	9,057 (9.5%)	-0.014
ORX - 1st and 2nd Generation SUs ; n (%)	1,054 (4.9%)	1,597 (5.2%)	-0.0137	1,837 (5.0%)	3,494 (5.4%)	-0.0180	2,891 (4.9%)	5,091 (5.3%)	-0.018
ORX - Insulins ; n (%)	897 (4.1%)	1,355 (4.4%)	-0.0149	1,551 (4.2%)	2,879 (4.5%)	-0.0147	2,448 (4.2%)	4,234 (4.4%)	-0.010
ORX - Other antidiabetic medications use; n (%)	826 (3.8%)	1,179 (3.9%)	-0.0052	1,704 (4.6%)	3,252 (5.0%)	-0.0187	2,530 (4.3%)	4,431 (4.7%)	-0.019
ORX - PPIs or H2RAs use; n (%)*	5,118 (23.6%)	6,819 (22.3%)	0.0309	7,835 (21.3%)	13,897 (21.5%)	-0.0049	12,953 (22.2%)	20,716 (21.8%)	0.010
ORX - NSAIDs; n (%)*	3,492 (16.1%)	5,242 (17.1%)	-0.0269	6,115 (16.6%)	11,947 (18.5%)	-0.0500	9,607 (16.4%)	17,189 (18.1%)	-0.045
ORX - Use of opioids ; n (%)*	7,529 (34.7%)	10,709 (35.0%)	-0.0063	13,564 (36.9%)	23,859 (36.9%)	0.0000	21,093 (36.1%)	34,568 (36.3%)	-0.004
ORX - Use of antipsychotics ; n (%)*	992 (4.6%)	1,281 (4.2%)	0.0195	1,445 (3.9%)	2,380 (3.7%)	0.0105	2,437 (4.2%)	3,661 (3.8%)	0.020
ORX - Use of antidepressants ; n (%)	7,865 (36.3%)	10,356 (33.9%)	0.0503	12,794 (34.8%)	21,535 (33.3%)	0.0317	20,659 (35.4%)	31,891 (33.5%)	0.040
ORX - Use of anxiolytics/hypnotics; n (%)	2,098 (9.7%)	3,001 (9.8%)	-0.0034	3,956 (10.8%)	7,101 (11.0%)	-0.0064 0.0118	6,054 (10.4%)	10,102 (10.6%)	-0.007 0.026
ORX - Use of Page of P	3,680 (17.0%)	4,802 (15.7%)	0.0352	4,975 (13.5%)	8,461 (13.1%)	0.0118	8,655 (14.8%) 11,913 (20.4%)	13,263 (13.9%) 18,924 (19.9%)	0.026
ORX - Use of Benzodiazepines ; n (%)*	3,637 (16.8%)	5,129 (16.8%)		8,276 (22.5%)	13,795 (21.3%)				
ORX - Use of dementia meds ; n (%)*	546 (2.5%)	679 (2.2%)	0.0198	871 (2.4%)	1,357 (2.1%)	0.0202	1,417 (2.4%)	2,036 (2.1%)	0.020
ORX - Use of antiparkinsonian meds ; n (%)*	821 (3.8%)	997 (3.3%)	0.0270 0.0191	1,231 (3.4%)	2,000 (3.1%)	0.0169	2,052 (3.5%) 3,109 (5.3%)	2,997 (3.1%) 4,597 (4.8%)	0.022
ORX - Use of oral anticoagulants ; n (%)*	1,035 (4.8%)	1,345 (4.4%)	0.0191	2,074 (5.6%)	3,252 (5.0%)	0.0268	5,099 (8.7%)	6,998 (7.3%)	0.023
ORX - Use of antiplatelet agents ; n (%)*	1,438 (6.6%)	1,582 (5.2%)	0.0594	3,661 (10.0%)	5,416 (8.4%)	0.0554	3,039 (0.7%)	0,990 (7.5%)	0.052
LFS - Obesity; n (%)	1,630 (7.5%)	2,388 (7.8%)	-0.0113	1,578 (4.3%)	2,791 (4.3%)	0.0000	3,208 (5.5%)	5,179 (5.4%)	0.004
PFT - Spirometry test only; n (%)	4,594 (21.2%)	3,785 (12.4%)	0.2370	9,392 (25.6%)	10,035 (15.5%)	0.2519	13,986 (23.9%)	13,820 (14.5%)	0.240
PFT - Spirometry test only (Count - 180 days to 31 days before CED) *	7,554 (21.2/0)	3,703 (12.470)	0.2370	3,332 (23.070)	10,000 (10.0%)	0.2313	13,300 (23.370)	15,520 (14.570)	0.240
mean (sd)	0.22 (0.74)	0.13 (0.55)	0.1380	0.23 (0.70)	0.15 (0.53)	0.1289	0.23 (0.72)	0.14 (0.54)	0.141
	5.22 (0.77)	0.23 (0.33)		0.23 (0.70)	0.15 (0.55)		(/	(*******)	

median [IQR]	0.00 [0.00, 0.00]	0.00 [0.00, 0.00]	0.0000	0.00 [0.00, 0.00]	0.00 [0.00, 0.00]	0.0000	0.00 (0.72)	0.00 (0.54)	0.000
PFT - Spirometry test only (Count - 30 days to CED) *	0.00 [0.00, 0.00]	0.00 [0.00, 0.00]	0.0000	0.00 [0.00, 0.00]	0.00 [0.00, 0.00]	0.0000	0.00 (0.72)	0.00 (0.54)	0.000
mean (sd)	0.18 (0.62)	0.08 (0.41)	0.1903	0.20 (0.60)	0.09 (0.39)	0.2174	0.19 (0.61)	0.09 (0.40)	0.194
median [IQR]	0.00 [0.00, 0.00]	0.00 [0.00, 0.00]	0.0000	0.00 [0.00, 0.00]	0.00 [0.00, 0.00]	0.0000	0.00 (0.61)	0.00 (0.40)	0.000
PFT - Lung volume, Diffuse capacity, pulmonary stress testing (any); n (%)	2,852 (13.1%)	2,795 (9.1%)	0.1276	4,207 (11.5%)	5,282 (8.2%)	0.1109	7,059 (12.1%)	8,077 (8.5%)	0.119
Title Eding volume, Dinase capacity, paintonary stress testing (any), 11 (70)	2,032 (13.170)	2,755 (5.176)	0.1270	4,207 (11.576)	3,202 (0.270)	0.1103	7,033 (12.170)	0,017 (0.370)	0.113
HCU - Pulmonologist visit (180 to 1 day before CED); n (%)	290 (1.3%)	246 (0.8%)	0.0491	7,544 (20.5%)	8,804 (13.6%)	0.1843	7,834 (13.4%)	9,050 (9.5%)	0.123
HCU - Pulmonologist visit on CED; n (%)	43 (0.2%)	28 (0.1%)	0.0258	1,568 (4.3%)	1,216 (1.9%)	0.1388	1,611 (2.8%)	1,244 (1.3%)	0.106
HCU - Pulmonologist visit (Number of during CAP) *		, ,							
mean (sd)	0.08 (1.11)	0.05 (0.93)	0.0293	0.89 (2.39)	0.49 (1.77)	0.1902	0.59 (2.01)	0.35 (1.55)	0.134
median [IQR]	0.00 [0.00, 0.00]	0.00 [0.00, 0.00]	0.0000	0.00 [0.00, 0.00]	0.00 [0.00, 0.00]	0.0000	0.00 (2.01)	0.00 (1.55)	0.000
HCU - Number of Internal Medicine/Family Medicine Visits									
mean (sd)	7.62 (11.28)	6.95 (11.33)	0.0593	6.26 (10.74)	5.66 (9.03)	0.0605	6.76 (10.94)	6.07 (9.83)	0.066
median [IQR]	4.00 [1.00, 10.00]	3.00 [0.00, 9.00]	0.0885	4.00 [1.00, 8.00]	3.00 [1.00, 7.00]	0.1008	4.00 (10.94)	3.00 (9.83)	0.096
HCU - Number of Cardiologist visits									
mean (sd)	0.89 (3.16)	0.75 (2.76)	0.0472	0.81 (2.83)	0.67 (2.84)	0.0494	0.84 (2.96)	0.70 (2.81)	0.049
median [IQR]	0.00 [0.00, 0.00]	0.00 [0.00, 0.00]	0.0000	0.00 [0.00, 0.00]	0.00 [0.00, 0.00]	0.0000	0.00 (2.96)	0.00 (2.81)	0.000
HCU - Number of Emergency Department (ED) visits v3				-					
mean (sd)	0.47 (1.31)	0.42 (1.18)	0.0401	0.17 (1.10)	0.16 (1.10)	0.0091	0.28 (1.18)	0.24 (1.13)	0.035
median [IQR]	0.00 [0.00, 0.00]	0.00 [0.00, 0.00]	0.0000	0.00 [0.00, 0.00]	0.00 [0.00, 0.00]	0.0000	0.00 (1.18)	0.00 (1.13)	0.000
HCU - Old hospitalization (-180 days to -31 days before CED); n (%)	1,883 (8.7%)	2,196 (7.2%)	0.0555	4,861 (13.2%)	7,875 (12.2%)	0.0300	6,744 (11.5%)	10,071 (10.6%)	0.029
HCU - Recent hospitalization (-30 days to CED date); n (%)	202 (0.9%)	264 (0.9%)	0.0000	595 (1.6%)	1,252 (1.9%)	-0.0229	797 (1.4%)	1,516 (1.6%)	-0.016
HCU - Number of hospitalizations during CAP									
mean (sd)	0.11 (0.38)	0.09 (0.35)	0.0547	0.16 (0.43)	0.16 (0.43)	0.0000	0.14 (0.41)	0.14 (0.41)	0.000
median [IQR]	0.00 [0.00, 0.00]	0.00 [0.00, 0.00]	0.0000	0.00 [0.00, 0.00]	0.00 [0.00, 0.00]	0.0000	0.00 (0.41)	0.00 (0.41)	0.000
HCU - Blood eosinophilia or Serum IgE test order; n (%)*	109 (0.5%)	161 (0.5%)	0.0000	145 (0.4%)	299 (0.5%)	-0.0149	254 (0.4%)	460 (0.5%)	-0.015
HCU - Pneumococcal vaccine; n (%)	2,791 (12.9%)	3,065 (10.0%)	0.0912	2,119 (5.8%)	2,509 (3.9%)	0.0885	4,910 (8.4%)	5,574 (5.9%)	0.097
HCU - Flu vaccine ; n (%)	4,134 (19.1%)	5,214 (17.1%)	0.0520	4,507 (12.3%)	6,971 (10.8%)	0.0469	8,641 (14.8%)	12,185 (12.8%)	0.058
HCU - Bone mineral density ; n (%)	988 (4.6%)	1,210 (4.0%)	0.0296	1,146 (3.1%)	1,659 (2.6%)	0.0301	2,134 (3.7%)	2,869 (3.0%)	0.039
HCU - Pap smear ; n (%)	817 (3.8%)	1,594 (5.2%)	-0.0676	1,625 (4.4%)	4,095 (6.3%)	-0.0845	2,442 (4.2%)	5,689 (6.0%)	-0.082
HCU - Mammogram ; n (%)	2,744 (12.7%)	3,954 (12.9%)	-0.0060	3,874 (10.5%)	7,572 (11.7%)	-0.0382	6,618 (11.3%)	11,526 (12.1%)	-0.025
HCU - Prostate exam for DRE; n (%)	694 (3.2%)	751 (2.5%)	0.0421	666 (1.8%)	767 (1.2%)	0.0494	1,360 (2.3%)	1,518 (1.6%)	0.051
HCU - Number of Echocardiogram *									
mean (sd)	0.20 (1.26)	0.17 (1.13)	0.0251	0.22 (0.79)	0.21 (0.80)	0.0126	0.21 (0.99)	0.20 (0.92)	0.010
median [IQR]	0.00 [0.00, 0.00]	0.00 [0.00, 0.00]	0.0000	0.00 [0.00, 0.00]	0.00 [0.00, 0.00]	0.0000	0.00 (0.99)	0.00 (0.92)	0.000
HCU - Flexible Sigmoidoscopy or colonoscopy or CT virtual colonoscopy ; n (%)	992 (4.6%)	1,258 (4.1%)	0.0245	1,950 (5.3%)	3,230 (5.0%)	0.0136	2,942 (5.0%)	4,488 (4.7%)	0.014
HCU - Number of Distinct Medication Prescriptions (not generalized to generics)									
mean (sd)	20.64 (17.20)	20.20 (16.75)	0.0259	19.54 (14.98)	19.61 (15.46)	-0.0046	19.95 (15.84)	19.80 (15.89)	0.009
median [IQR]	16.00 [9.00, 27.00]	16.00 [9.00, 27.00]	0.0000	16.00 [9.00, 26.00]	16.00 [9.00, 26.00]	0.0000	16.00 (15.84)	16.00 (15.89)	0.000
CCC Constitution of the second									
SES - Copay for pharmacy cost (charges in U.S. \$)	22.22.423	22 47 (25 22)	-0.0341	25.22.(25.21)	0.5 0.5 (0.5 10)	0.0057	28.43 (31.20)	28.43 (29.95)	0.000
mean (sd)	32.20 (38.19)	33.47 (36.20)	-0.0341	26.20 (26.21)	26.05 (26.49)	-0.0065	28.43 (31.20)	28.43 (29.95)	-0.021
median [IQR]	23.64 [9.89, 41.20]	25.69 [12.25, 43.02]	-0.0551	20.87 [10.38, 35.00]	21.04 [10.00, 35.00]	-0.0065	21.90 (31.20)	22.53 (29.95)	-0.021
SES - Business type	6 607 (20 00%)	42.426.442.000	-0.2527		1	+	C CO7 (20 00()	42.426.442.050	-0.253
Commercial; n (%)	6,697 (30.9%) 14,992 (69.1%)	13,136 (43.0%) 17,434 (57.0%)	0.2527		1	+	6,697 (30.9%) 14.992 (69.1%)	13,136 (43.0%) 17,434 (57.0%)	0.253
Medicare; n (%)		, , , , , , , , , , , , , , , , , , , ,	0.2527		1	+	4,586 (21.1%)	17,434 (57.0%) 4,970 (16.3%)	0.253
SES - Low income indicator ; n (%)	4,586 (21.1%)	4,970 (16.3%)	0.1233			+	4,586 (21.1%)	4,970 (16.3%)	0.123
SES - Insurance Plan type		+	+	10,656 (29.0%)	16,804 (26.0%)	0.0672	10,656 (29.0%)	16 904 (26 000)	0.067
Comprehensive; n (%)		+	+			-0.0303		16,804 (26.0%)	-0.030
HMO; n (%)			+ +	4,376 (11.9%)	8,310 (12.9%)		4,376 (11.9%)	8,310 (12.9%)	
PPO; n (%)			+ +	17,092 (46.5%)	30,849 (47.7%)	-0.0240	17,092 (46.5%)	30,849 (47.7%)	-0.024 -0.027
Others; n (%)		l	1 1	4,603 (12.5%)	8,690 (13.4%)	-0.0268	4,603 (12.5%)	8,690 (13.4%)	-0.027

^{*} Not included in PS model

PS MATCHED	OPTUM			-	MARKETSCAN	POOLED			
Number of patients	Referent - Tiotropium 18,017	Exposure - Salmeterol/Fluticasone 18,017	St. Diff	Referent - Tiotropium 31,122	Exposure - Salmeterol/Fluticasone 31,122	St. Diff	Referent - Tiotropium 49,139	Exposure - Salmeterol/Fluticasone 49,139	e St. Diff
Calendar Time - Year of Initiation (2004 - 2020)	18,017	18,017		31,122	31,122		49,139	49,139	+
2004-2006; n (%)	1,289 (7.2%)	1,219 (6.8%)	0.0157	5,326 (17.1%)	5,292 (17.0%)	0.0027	6,615 (13.5%)	6,511 (13.3%)	0.006
2007-2008; n (%)	2,030 (11.3%)	2,065 (11.5%)	-0.0063	5,203 (16.7%)	5,279 (17.0%)	-0.0080	7,233 (14.7%)	7,344 (14.9%)	-0.006
2009-2011; n (%)	3,594 (19.9%)	3,602 (20.0%)	-0.0025	8,529 (27.4%)	8,599 (27.6%)	-0.0045	12,123 (24.7%)	12,201 (24.8%)	-0.002
2012-2015; n (%)	5,440 (30.2%)	5,414 (30.0%)	0.0044	9,009 (28.9%)	8,912 (28.6%)	0.0066	14,449 (29.4%)	14,326 (29.2%)	0.004
2016-2018; n (%)	3,880 (21.5%)	3,887 (21.6%)	-0.0024	3,055 (9.8%)	3,040 (9.8%)	0.0000	6,935 (14.1%)	6,927 (14.1%)	0.000
2019-Mar. 2020; n (%)	1,784 (9.9%)	1,830 (10.2%)	-0.0100				1,784 (9.9%)	1,830 (10.2%)	-0.010
DMG - Age									+
mean (sd)	67.43 (10.50)	67.84 (11.57)	-0.0371	65.64 (11.34)	66.01 (12.78)	-0.0306	66.30 (11.04)	66.68 (12.35)	-0.032
median [IQR]	68.00 [60.00, 75.00]	69.00 [60.00, 76.00]	-0.0905	64.00 [58.00, 74.00]	65.00 [57.00, 76.00]	-0.0828	65.47 (11.04)	66.47 (12.35)	-0.085
DMG - Gender							10.000 (00.00)		
Male; n (%)	6,330 (35.1%)	6,304 (35.0%)	0.0021	12,025 (38.6%)	12,000 (38.6%)	0.0000	18,355 (37.4%)	18,304 (37.2%)	0.004
Female; n (%) DMG - Geographic region	11,687 (64.9%)	11,713 (65.0%)	-0.0021	19,097 (61.4%)	19,122 (61.4%)	0.0000	30,784 (62.6%)	30,835 (62.8%)	-0.004
Northeast: n (%)	1,731 (9.6%)	1,705 (9.5%)	0.0034	4,713 (15.1%)	4,752 (15.3%)	-0.0056	6,444 (13.1%)	6,457 (13.1%)	0.000
South; n (%)	8,144 (45.2%)	8,102 (45.0%)	0.0040	11,758 (37.8%)	11,766 (37.8%)	0.0000	19,902 (40.5%)	19,868 (40.4%)	0.002
North Central; n (%)	3,811 (21.2%)	3,855 (21.4%)	-0.0049	10,606 (34.1%)	10,593 (34.0%)	0.0021	14,417 (29.3%)	14,448 (29.4%)	-0.002
West; n (%)	4,331 (24.0%)	4,355 (24.2%)	-0.0047	4,045 (13.0%)	4,011 (12.9%)	0.0030	8,376 (17.0%)	8,366 (17.0%)	0.000
DRS - Combined comorbidity score, 180 days									1
mean (sd)	1.37 (1.71)	1.38 (1.78)	-0.0057	1.10 (1.45)	1.10 (1.52)	0.0000	1.20 (1.55)	1.20 (1.62)	0.000
median [IQR]	1.00 [0.00, 2.00]	1.00 [0.00, 2.00]	0.0000	1.00 [0.00, 2.00]	1.00 [0.00, 2.00]	0.0000	1.00 (1.55)	1.00 (1.62)	0.000
DRS - Frailty Score: Empirical Version (mean)								2 4 7 (2 2 2)	
mean (sd)	0.18 (0.06)	0.18 (0.06)	0.0000	0.17 (0.05)	0.17 (0.06)	0.0000	0.17 (0.05)	0.17 (0.06)	0.000
median [IQR]	0.17 [0.14, 0.21]	0.17 [0.14, 0.21]	0.0000	0.16 [0.13, 0.19]	0.15 [0.13, 0.19]	0.1811	0.16 (0.05)	0.16 (0.06)	0.000
PLM - Smoking ; n (%)	4,968 (27.6%)	4,844 (26.9%)	0.0157	4,977 (16.0%)	4,803 (15.4%)	0.0165	9,945 (20.2%)	9,647 (19.6%)	0.015
PLM - Pneumonia ; n (%)	1,122 (6.2%)	1,104 (6.1%)	0.0042	2,335 (7.5%)	2,288 (7.4%)	0.0038	3,457 (7.0%)	3,392 (6.9%)	0.004
PLM - Oxygen usage; n (%)	1,135 (6.3%)	1,127 (6.3%)	0.0000	2,474 (7.9%)	2,436 (7.8%)	0.0037	3,609 (7.3%)	3,563 (7.3%)	0.000
PLM - Respiratory arrest/dependence on oxygen ; n (%)	452 (2.5%)	452 (2.5%)	0.0000	791 (2.5%)	735 (2.4%)	0.0065	1,243 (2.5%)	1,187 (2.4%)	0.006
PLM - CiPAP/BiPAP use; n (%)	706 (3.9%)	715 (4.0%)	-0.0051	1,569 (5.0%)	1,544 (5.0%)	0.0000	2,275 (4.6%)	2,259 (4.6%)	0.000
PLM - Pulmonary rehabilitation ; n (%)*	49 (0.3%)	36 (0.2%)	0.0200	99 (0.3%)	78 (0.3%)	0.0000	148 (0.3%)	114 (0.2%)	0.020
PLM - Moderate COPD exacerbation - [Count with 365 to 181 days before CED]*									
mean (sd)	1.27 (2.69)	1.30 (2.75)	-0.0110	0.98 (2.17)	0.97 (2.04)	0.0047	1.09 (2.37)	1.09 (2.33)	0.000
median [IQR]	0.22 [0.00, 1.35]	0.27 [0.00, 1.40]	-0.0184	0.01 [0.00, 1.00]	0.05 [0.00, 1.00]	-0.0190	0.09 (2.37)	0.13 (2.33)	-0.017
PLM - Moderate COPD exacerbation - [Count 180 to 31 days before CED]*mean (sd)	0.86 (1.93)	0.82 (1.84)	0.0212	0.63 (1.44)	0.62 (1.42)	0.0070	0.71 (1.64)	0.69 (1.59)	0.012
median (su)	0.00 [0.00, 0.95]	0.00 [0.00, 0.93]	0.0000	0.00 [0.00, 0.75]	0.00 [0.00, 0.75]	0.0000	0.00 (1.64)	0.00 (1.59)	0.000
PLM - Moderate COPD exacerbation - [Count with 30 days to CED]*	0.00 [0.00, 0.93]	0.00 [0.00, 0.93]	0.0000	0.00 [0.00, 0.73]	0.00 [0.00, 0.73]	0.0000	0.00 (1.04)	0.00 (1.55)	0.000
mean (sd)	0.02 (0.10)	0.01(0.09)	0.1051	0.01 (0.08)	0.01 (0.08)	0.0000	0.01 (0.09)	0.01 (0.08)	0.000
median [IQR]	0.00 [0.00, 0.00]	0.00 [0.00, 0.00]	0.0000	0.00 [0.00, 0.00]	0.00 [0.00, 0.00]	0.0000	0.00 (0.09)	0.00 (0.08)	0.000
PLM - Moderate exacerbations >=1 in 365 days before CED; n (%)	12,493 (69.3%)	12,555 (69.7%)	-0.0087	19,559 (62.8%)	19,638 (63.1%)	-0.0062	32,052 (65.2%)	32,193 (65.5%)	-0.006
PLM - Moderate exacerbations >= 2 in 365 days before CED; n (%)	7,747 (43.0%)	7,755 (43.0%)	0.0000	11,085 (35.6%)	11,239 (36.1%)	-0.0104	18,832 (38.3%)	18,994 (38.7%)	-0.008
PLM - Severe COPD exacerbation - [Count with 365 to 181 days before CED] *									
mean (sd)	0.03 (0.18)	0.03 (0.18)	0.0000	0.05 (0.21)	0.05 (0.21)	0.0000	0.04 (0.20)	0.04 (0.20)	0.000
median [IQR] PLM - Severe COPD exacerbation - [Count with 180 to 31 days before CED] *	0.00 [0.00, 0.00]	0.00 [0.00, 0.00]	0.0000	0.00 [0.00, 0.00]	0.00 [0.00, 0.00]	0.0000	0.00 (0.20)	0.00 (0.20)	0.000
PLM - Severe COPD exacerbation - [Count with 180 to 31 days before CED] *mean (sd)	0.02 (0.14)	0.02 (0.13)	0.0000	0.03 (0.15)	0.03 (0.15)	0.0000	0.03 (0.15)	0.03 (0.14)	0.000
median (Su)	0.02 (0.14)	0.00 [0.00, 0.00]	0.0000	0.00 [0.00, 0.00]	0.00 [0.00, 0.00]	0.0000	0.00 (0.15)	0.00 (0.14)	0.000
PLM - Severe COPD exacerbation - [Count with 30 days lookback] *	0.00 [0.00, 0.00]	0.00 [0.00, 0.00]	0.0000	0.00 [0.00, 0.00]	0.00 [0.00, 0.00]	3.0000	0.00 (0.13)	0.00 (0.1-1)	+ 0.000
mean (sd)	0.00 (0.01)	0.00 (0.01)	0.0000	0.00 (0.01)	0.00 (0.01)	0.0000	0.00 (0.01)	0.00 (0.01)	0.000
median [IQR]	0.00 [0.00, 0.00]	0.00 [0.00, 0.00]	0.0000	0.00 [0.00, 0.00]	0.00 [0.00, 0.00]	0.0000	0.00 (0.01)	0.00 (0.01)	0.000
PLM - Severe exacerbations >=1 in 365 days before CED; n (%)	1,038 (5.8%)	1,015 (5.6%)	0.0086	2,595 (8.3%)	2,650 (8.5%)	-0.0072	3,633 (7.4%)	3,665 (7.5%)	-0.004
PLM - Severe exacerbations >=2 in 365 days before CED ; n (%)	93 (0.5%)	86 (0.5%)	0.0000	198 (0.6%)	198 (0.6%)	0.0000	291 (0.6%)	284 (0.6%)	0.000
PLM - GOLD C/D Status ; n (%)	5,385 (29.9%)	5,395 (29.9%)	0.0000	9,771 (31.4%)	9,873 (31.7%)	-0.0065	15,156 (30.8%)	15,268 (31.1%)	-0.006
PRX - LABA only ; n (%)	93 (0.5%)	99 (0.5%)	0.0000	348 (1.1%)	332 (1.1%)	0.0000	441 (0.9%)	431 (0.9%)	0.000
